## List of abbreviations

Term	Definition / description
BMI	Body mass index
CDR	Cause-of-Death register
CI	Confidence interval
eGFR	Estimated glomerular filtration rate
HbA1c	Glycated haemoglobin A1c
HDL	High Density Lipoprotein
ICD-10	International classification of diseases
MI	Myocardial infarction
NDR	National diabetes register
NPR	National patient register
PH	Proportional hazards
PS	Propensity score
RR	Relative risk
SPDR	Swedish prescribed drug register

- T1DM Type 1 diabetes mellitus
- T2DM Type 2 diabetes mellitus

## Introduction

The Swedish National Diabetes Register (NDR) was launched in 1996 for the purpose of promoting evidence-based development of diabetes care. The NDR has been online since April 2002 (www.ndr.nu), allowing individual clinics to quickly monitor their activities on a regular basis. The register offers a unique opportunity to monitor the quality of care in terms of risk factors and the potential complications of diabetes. The results generated by the register have been presented at many international meetings and conferences. To our knowledge, the NDR is the largest diabetes register in the world.

Patients with Type 2 diabetes mellitus (T2DM) are at high risk for developing cardiovascular disease (CVD) complications.

The EMPA-REG OUTCOME (ERO) trial demonstrated a reduction in cardiovascular death, hospitalization from heart failure and all-cause mortality. Empagliflozin also reduces the risk for new onset or worsening of nephropathy, progression to macroalbuminuria and doubling of serum creatinine accompanied by eGFR of  $\leq$ 45 ml/min/1,73 m^2. Empagliflozin is also associated with weight loss. (1)

In the ERO patients had a history of CV disease. (Appendix 1). It is not known how many of patients in clinical practice have a history of CV disease according to the ERO definition. In a publication by Norhammar et al patients with CVD was approximately 34 %. (2)However those data also included patients with atrial fibrillation and excluded patients with peripheral artery disease.

According to newly published Swedish guidelines by both the National board of Health and Welfare and the Medical Products Agency patients with type 2 diabetes and cardiovascular disease start treatment with Empagliflozin. (3) It is not known how many patients with T2DM and cardiovascular disease receive empagliflozin today.

## Research question and objectives

### Research questions

- 1. Describe the prevalence of T2DM patients with established CVD according to ERO study definition in a Swedish population. (Appendix 1).
- 2. Describe the prevalence of established CVD according to ERO study definition in patients with T2DM who initiates treatment with empagliflozin.

### Objectives

### Primary objectives

- 1. To estimate the point prevalence of cardiovascular disease among persons with T2DM at 2017-12-31.
- 2. To estimate the prevalence of cardiovascular disease among persons with T2DM who initiates treatment with empagliflozin between 2015-01-01 and 2017-12-31

#### Secondary objectives

- 1. Describe the T2DM patients with established CVD according to ERO study definition with respect to demographics and disease characteristics.
- 2. Describe the patients initiating with empagliflozin with respect to demographics and disease characteristics.

## Subject sets analyzed

Source population in the study

The broad study population will include patients with T2DM and at least one registration in the NDR (at any time from start of registry until 2017) and who are alive on 2015-01-01. Based on this population, the following two sub-populations will be identified, corresponding to each of the two research questions:

Population	Definition	Details	Data source
Broad population	Patients with T2DM and at least one registration in the NDR (at any time from start of registry until 2017) and alive on 2015-01-01		NDR
Population 1	Among the broader study population, those who are alive also on 2017-12-31 will be included.		NDR
Population 2	Among the broader study population, those	SPDR used to	NDR

Table 1 Populations

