#### Table 2 Data sources with look-back periods and total data collection periods

#### Table 3 Established CVD

Variable	Definition	Details	Data source
Established CVD	Presence of at least one of the ICD10 codes as defined in appendix 1	NPR introduced ICD10-codes in 1997, i.e. data from that year and later will be used	NPR inpatient and outpatient

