## Planned analysis

### Summary of study populations identification

The identification process used to identify the study populations and subgroups will be summarized using population flowcharts including the following information:

- The total number of patients in the broad population (i.e. patients with T2DM and with at least one registration in the NDR and who are alive on 2015-01-01).
- The number of patients who are also alive on 2017-12-31 (the population for Question 1).
- The number of patients collecting Empagliflozin between 2015-01-01 and 2017-12-31 but who are not part of the broad population
- The number of patients in the broad population initiating Empagliflozin between 2015-01-01 and 2017-12-31 (the population for question 2)

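### Population 1 has no residence condition on 2017-12-31: if the target is people living in Sweden, registered emigrants not recorded as dead stay in the denominator of primary objective 1

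*Combined protocol and SAP*

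**What the plan says.** All references are to the combined protocol and SAP.

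- **Broad population** (Subject sets analyzed, Table 1): "Patients with T2DM and at least one registration in the NDR (at any time from start of registry until 2017) and alive on 2015-01-01".
- **Population 1** (same table): "Among the broader study population, those who are alive also on 2017-12-31 will be included". The flowchart list under Summary of study populations identification repeats this rule and adds no further step: "The number of patients who are also alive on 2017-12-31 (the population for Question 1").
- **Target.** Research question 1 is to "Describe the prevalence of T2DM patients with established CVD according to ERO study definition in a Swedish population". Primary objective 1 is "To estimate the point prevalence of cardiovascular disease among persons with T2DM at 2017-12-31". The Introduction gives the motivation: "It is not known how many of patients in clinical practice have a history of CV disease according to the ERO definition".
- **Data sources** (Table 2): NDR, prescribed drug register, NPR and Cause-of-Death register. None is described as giving residence or migration. The one-year NDR look-back serves to characterise patients and is not an entry condition.
- **Established CVD** (Table 3): "Presence of at least one of the ICD10 codes as defined in appendix 1", taken from the inpatient and outpatient NPR from 1997 onwards.
- **Output** (Main analysis): both the count and the percentage with established CVD are reported.

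**The concern.** A point prevalence is defined by who belongs to the population on the chosen date. Here one registration at any time since the register began is enough, provided the person is alive on 2017-12-31. Someone registered years ago who has since left Sweden still qualifies unless recorded as dead. If research question 1 is about people living in Sweden, that person is in the denominator but outside the target.

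The numerator may be affected too. NPR codes from before departure still count, whereas CVD that arises abroad may not be recorded there. Emigrants could therefore have a recorded CVD share different from that of residents, which would move the percentage. Even where the percentage does not move, the reported counts would include people outside the target. No planned output would show how many.

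The point is confined to Population 1. Population 2 is tied to a drug collection recorded in the Swedish prescribed drug register on its own index date.

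**Working it through.** The plan gives no expected denominator, prevalence assumption or emigration figure, so there is no figure of its own to reproduce. The check has two parts.

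**1. Does anything in the plan remove emigrants?**

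| Place | Condition on Population 1 | Removes emigrants? |
|---|---|---|
| Table 1, broad population | T2DM, one NDR registration up to 2017, alive on 2015-01-01 | No |
| Table 1, Population 1 | Alive on 2017-12-31 | No |
| Flowchart list | Alive on 2017-12-31 | No |
| Table 2, NDR look-back of 1 year | Describes patients; not an entry rule | No |
| Table 2, Cause-of-Death register | Establishes that patients are alive | No |

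Table 1 is incomplete in the text available, but this does not affect the result, because the flowchart list restates the Population 1 rule.

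**2. How large could the effect be?**

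Inputs:
- p, CVD prevalence among residents: 34%, the background figure in the Introduction. It rests on a different CVD definition ("those data also included patients with atrial fibrillation and excluded patients with peripheral artery disease"), so it only sets the scale.
- f, share of Population 1 that had emigrated: not in the documents; assumed.
- q, share of those emigrants with a qualifying NPR code: not in the documents; assumed 0 to 40%.

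Reported prevalence = (1 - f) × p + f × q, so shift = f × (q - p).

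With p = 34%:

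| f | q = 0 | q = 10% | q = 34% | q = 40% |
|---|---|---|---|---|
| 0.5% | -0.17 | -0.12 | 0 | +0.03 |
| 1% | -0.34 | -0.24 | 0 | +0.06 |
| 2% | -0.68 | -0.48 | 0 | +0.12 |

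(Percentage points. For example, 0.01 × (0 - 0.34) = -0.0034, or -0.34 points.)

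The result is not very sensitive to p. At f = 1%, p = 25% gives 0.01 × (0 - 0.25) = -0.25 to 0.01 × (0.40 - 0.25) = +0.15 points, and p = 40% gives -0.40 to 0 points.

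The emigrated share needed for a 1-point shift is f = 0.01 / |q - p|. With p = 34%:
- q = 0: 0.01 / 0.34 = 2.9%
- q = 10%: 0.01 / 0.24 = 4.2%
- q = 20%: 0.01 / 0.14 = 7.1%
- q = 40%: 0.01 / 0.06 = 16.7%

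The denominator count is too high by f / (1 - f), about 1.0% at f = 1%. This only restates the assumed f.

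**The case against.** **The target is a matter of reading.** Primary objective 1 has no residence term. The Swedish population of research question 1 could mean people in Swedish registers, and the Introduction's reference to clinical practice does not define residence either. This stands, and it is why the point is conditional. It does not remove the point: the plan does not say which population is meant, and a prevalence at a single date needs that settled.

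**Table 2 lists sources and periods, not data fields.** The linked data might carry an emigration flag. That is possible, but the stated rule and the flowchart would still make no use of it.

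**The effect is probably small.** This largely stands. The larger shifts need several per cent emigrated together with almost no CVD coded before departure, and the codes count from 1997 onwards. The analysis is descriptive, with no hypothesis test depending on the estimate.

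**Stronger readings a reader might infer.** One is that the plan will underestimate CVD prevalence. The documents do not support this: the sign depends on whether recorded CVD is lower among emigrants than among residents, and neither share is given. Another is that CVD recording ends when a person leaves. No section says what the NPR holds after departure, so incomplete capture is only an assumption.

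**Conclusion.** The point holds in conditional form. Followed as written, the plan defines Population 1 by an NDR registration at any time and survival to 2017-12-31. If the intended target is people living in Sweden on that date, the rule misses it, because registered emigrants not recorded as dead are retained.

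The size and direction of the effect on the percentage cannot be set from the documents. Within the assumed inputs a fraction of a percentage point is the plausible order of magnitude. A full point would need an emigrated share of about 3% or more, and that minimum applies only if none of the emigrants had a qualifying code. The figures rest on a borrowed 34% and on assumed values of f and q.

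The change is worth making because this is one of two primary estimates, the remedy is inexpensive, and nothing in the planned output would let a reader judge how many such persons are included.

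**What to change.** **Preferred change.** Add residence in Sweden on 2017-12-31 to the Population 1 definition in Table 1, excluding persons recorded as emigrated and not returned. Add a flowchart step showing the number excluded. The cost is one eligibility line and one count, provided migration dates can be obtained in the linkage.

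**If migration dates cannot be obtained.** Beside the primary estimate, report a sensitivity row limited to Population 1 members with a recent NDR registration, for example in 2016-2017. Give the number removed and their recorded CVD share, and state that residence was not verified. The row uses NDR data already in the study. The limitation sentence alone would not be enough, because it leaves the reader with nothing to gauge the effect by.

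**Downside.** The sensitivity row also drops eligible residents without a recent registration, and it keeps anyone who emigrated after a recent entry. It does not isolate emigration and cannot replace the primary estimate. The two-year window is an example and is not derived from the plan, so it should be fixed before the data are analysed.

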### Index date

The index date for question 1 will be 2017-12-31. For question 2, the index date will be the date corresponding to the first collection of empagliflozin.

### Baseline and look back period

To characterize the study population, all information available during the look-back (preindex) time period will be collected.

The look-back time period is defined as the time period ending on the day before the index date (Table 2).

Data source	Data holder	Look-back period	Total data collection period
National diabetes register (NDR)	Centre of Registers, Region Västra Götaland	1 year	1996-2017
Swedish prescribed drug register (SPDR)	National Board of Health and Welfare		2015.01.01- 2017.12.31
National patient register (NPR), both inpatient  and outpatient  registers	National Board of Health and Welfare	1997-index date (i.e. as long as data allows)	1997-2017
Cause of death register (CDR)	National board of health and welfare	Will be used to establish the broader population and population 2 (i.e to establish that patients are alive)	2017

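### Does the plan need extra analyses because NDR registration may follow the first empagliflozin collection, and because Table 5 uses one year of NDR data?

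*Combined protocol and SAP*

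**What the plan says.** **Entry.** Under Subject sets analyzed, the broad population consists of T2DM patients alive on 2015-01-01 with "at least one registration in the NDR (at any time from start of registry until 2017").

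**Index.** The section Index date says: "For question 2, the index date will be the date corresponding to the first collection of empagliflozin". For question 1 the index date is 2017-12-31.

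**Population 2.** The flowchart list under Summary of study populations identification gives it as "The number of patients in the broad population initiating Empagliflozin between 2015-01-01 and 2017-12-31 (the population for question 2"). The defining row in Table 1 is incomplete in the text available here. The same list also plans this count: "The number of patients collecting Empagliflozin between 2015-01-01 and 2017-12-31 but who are not part of the broad population".

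**Look-back.** Its stated purpose is descriptive: "To characterize the study population, all information available during the look-back (preindex) time period will be collected". Its end point is fixed by "The look-back time period is defined as the time period ending on the day before the index date (Table 2"). Table 2 allows one year for the NDR. For the NPR, the source of established CVD, it allows "1997-index date (i.e. as long as data allows").

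**Reporting.** Main analysis reports Table 5 for patients with established CVD in Population 1 and for everyone in Population 2. All 20 rows of Table 5 name the NDR as source. There is no hypothesis testing.

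**The concern.** The second primary objective is "To estimate the prevalence of cardiovascular disease among persons with T2DM who initiates treatment with empagliflozin between 2015-01-01 and 2017-12-31". If registration may come after index, membership of that denominator depends partly on a later event. An initiator without an earlier registration is counted only if he or she is registered by the end of 2017. One who dies first, or is never registered, is not counted. The planned count of collectors outside the broad population does not show late registrants, because they are inside it. A reader could not tell how many there are or whether the prevalence depends on them.

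The second strand concerns Table 5. Entry accepts a registration from any year, but the values come from one year. A patient last registered in 2012 who first collects empagliflozin on 2016-03-01 belongs to Population 2 and has no NDR value in the window. The visible text gives no rule for such patients and does not promise the number with data for each row. The clinical rows might then be read as describing the whole group when they describe recent registrants.

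**Working it through.** The plan gives no sample size, power or expected prevalence for this point, so there is no figure of its own to reproduce.

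**1. Can registration follow index?** Inputs: NDR data 1996-2017 (Table 2) and initiation from 2015-01-01 to 2017-12-31 (Primary objectives). The documents give only the year the register began, so a start on 1996-01-01 is assumed. The entry period is then 22 × 365 + 6 leap days = 8,036 days. Days before index + 1 index day + days after index must equal 8,036:

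| Index date | Days before | Days after |
|---|---|---|
| 2015-01-01 | 6,940 | 1,095 |
| 2016-01-01 | 7,305 | 730 |
| 2017-01-01 | 7,671 | 364 |
| 2017-12-31 | 8,035 | 0 |

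As an example, a first collection on 2015-06-01 with a first registration on 2017-11-01 meets the flowchart wording. So late registration is possible on the visible text. These days say nothing about how many patients are involved. For question 1 the issue cannot arise, because entry and index both end on 2017-12-31.

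**2. Is CVD status affected?** No. Table 3 takes it from the NPR, and Table 2 runs the NPR look-back from 1997 to index. A late NDR registration does not alter that record.

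**3. How large could the shift be?** Let f be the share of Population 2 first registered after index, and p_late and p_other the CVD prevalences in late registrants and in the rest.

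Shift = (1 − f) × p_other + f × p_late − p_other = f × (p_late − p_other)

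Neither f nor the difference is in the documents. With assumed values:

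| f | Difference 10 points | Difference 20 points |
|---|---|---|
| 1% | 0.1 | 0.2 |
| 5% | 0.5 | 1.0 |
| 10% | 1.0 | 2.0 |

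The shift is in percentage points and may go either way. The base prevalence cancels. For example, with the 34% cited in the Introduction (for a different CVD definition), f = 10% and p_late = 54%: 0.9 × 34 + 0.1 × 54 = 36.0, a shift of 2.0. These are illustrations, not evidence of an effect.

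**4. Would a comparison with and without late registrants help?** It shows whether the figure depends on them. It does not recover initiators who died or stayed unregistered. Those already fall in the planned count of collectors outside the broad population, mixed with others.

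**5. Table 5.** It has 20 rows. Setting aside age, sex and diabetes duration, on the assumption that any NDR record can supply them, leaves 20 − 3 = 17. Read literally, the window covers all 20. For Population 1 the window runs from 2016-12-31 to 2017-12-30, 365 days. Patients without a record in it have missing values; they do not leave the population.

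A three-year window would be feasible, since from the earliest index it starts on 2012-01-01, within the NDR data. But Table 5 evaluates its variables at the index date, so older values are further from what is being described. Comparing CVD prevalence between patients with and without a recent NDR record would not settle the matter for Population 1: there Table 5 covers CVD patients only, and the comparison does not show whether their HbA1c or BMI values are representative.

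**The case for a change.** The strongest case for acting is this. Objective 2 is primary, and the study is purely descriptive, so who is counted is the result. The flowchart sentence is complete and labels itself as the question 2 population, yet has no timing condition. Table 5 is promised for all of Population 2, while the window may leave some of them without values. The data are already planned for collection, so one sentence, one count and the number with data per row would cost little.

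Some of this stands. On the visible text late registration is allowed, the existing count does not reveal it, and readers need the number with data to interpret each row.

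The rest does not carry the point to a change:

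- The flowchart list is not the definition. The CDR row of Table 2 mentions establishing that patients in Population 2 are alive, which the list does not repeat. The list may therefore be abbreviated, although that row could also be a slip for Population 1. A condition cannot be called absent when the row that would hold it is cut off.
- Late registrants can be genuine T2DM initiators with a full NPR history. Removing them would leave out people the objective means to include.
- Nothing in the plan rules out showing the number with data, and a descriptive table normally carries it.

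**Conclusion.** No change to the plan follows. On registration timing, the apparent gap rests on an incomplete table row. If the full row is also silent, the literal reading, in which any registration up to the end of 2017 qualifies, is workable and defensible. Analysts can state in the report which reading they applied. On Table 5, one year is a fair trade of completeness for recency, and the number with data per row is routine output that needs no amendment. A longer look-back, a prevalence without late registrants and a comparison by recent NDR record are optional extras; none corrects a wrong result.

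CVD classification is unaffected. The effect on the objective 2 prevalence cannot be derived, and the illustrated 0.1 to 2.0 points rests wholly on assumed shares and differences. The Table 5 strand touches the secondary objectives only. The conclusion would need another look if late registrants turned out to be a large share of Population 2.

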#### Table 2 Data sources with look-back periods and total data collection periods

#### Table 3 Established CVD

Variable	Definition	Details	Data source
Established CVD	Presence of at least one of the ICD10 codes as defined in appendix 1	NPR introduced ICD10-codes in 1997, i.e. data from that year and later will be used	NPR inpatient and outpatient

## Initiation on Empagliflozin

#### Table 4 Initiation of empagliflozin

Variable	Definition	Details	Data source
Date for initiation of empagliflozin	The date for first collection of Empagliflozin (ATC code A10BK03)	Index date for Question 2	SPDR

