## Main analysis

All analyses will be descriptive and no testing of hypotheses will be performed. The number and percentage of subjects with established CVD will be calculated and reported for both questions.

Variables in Table 5 will be descriptively reported for patients with established CVD within population 1 as well as for all patients in population 2.

Relating to question 2, the sub-group of patients initiating Empagliflozin during 2017 will be described with respect to prevalence of established CVD as well as the demographic and disease characteristics of Table 5.

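### The drug-register extract starts on the first day of the initiation window, so a first collection is only the first in the extract (low severity; the number of persons affected may be zero)

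*Combined protocol and SAP*

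**What the plan says.** Primary objective 2 concerns persons with T2DM "who initiates treatment with empagliflozin between 2015-01-01 and 2017-12-31". Table 4 defines the date of initiation as "The date for first collection of Empagliflozin (ATC code A10BK03", with SPDR as the source. The Index date section agrees: for question 2, "the index date will be the date corresponding to the first collection of empagliflozin".

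Table 2 gives the total data collection period for SPDR as "2015.01.01- 2017.12.31". The flowchart described under Summary of study populations identification is to report "The number of patients in the broad population initiating Empagliflozin between 2015-01-01 and 2017-12-31", and this group is the population for question 2.

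Under Main analysis, "the sub-group of patients initiating Empagliflozin during 2017 will be described with respect to prevalence of established CVD", and the Table 5 characteristics are reported for the same sub-group. The same section states: "All analyses will be descriptive and no testing of hypotheses will be performed".

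In the copy available for review, the Population 2 row of Table 1 breaks off and the SPDR look-back cell of Table 2 is blank. Neither is counted here as an error.

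**The concern.** To call a collection an initiation, one must be able to see that no collection came before it. With SPDR data that begin on the day the window opens, the earliest index dates have little or no prior drug history. A person already on the drug before 2015 who refilled in the window would look the same as a new user.

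The legible text has no washout, no criterion of no earlier collection and no flowchart step that removes earlier users. It also does not say that collection before 2015 was impossible. The diabetes drugs variable in Table 5 is a baseline descriptor and is not said to exclude anyone.

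The denominator of primary objective 2 is at stake, and in a purely descriptive study the population definition carries most of the weight. Secondary objective 2 is touched as well. For an earlier user, Table 5 values taken at a refill date, such as BMI, could be on-treatment values, and the Introduction itself says that the drug is associated with weight loss.

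**Working it through.** The plan states no figure on this point, so there is none to reproduce. The check has three parts.

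**1. Drug history visible before the index date.** Inputs: SPDR start 2015-01-01 (Table 2); window 2015-01-01 to 2017-12-31, or 1,096 days (Primary objectives). Visible history = index date minus 2015-01-01.

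| Index year | Minimum days | Maximum days |
|---|---|---|
| 2015 | 0 | 364 |
| 2016 | 365 | 730 |
| 2017 | 731 | 1,095 |

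An earlier user who continued without a long pause would collect again during 2015, so any misclassified persons would cluster there. To enter the 2017 sub-group, an earlier user would need 731 days without a collection.

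**2. Possible shift in the primary prevalence.** The documents give neither a count of earlier users nor their CVD prevalence, so both inputs are assumptions. Let r be the number of earlier users divided by the number of true initiators, and d the absolute difference in CVD prevalence between the two groups, in percentage points. Earlier users then make up r/(1+r) of the counted population, and

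shift = d × r/(1+r).

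| r | d = 5 | d = 10 | d = 15 |
|---|---|---|---|
| 0% | 0 | 0 | 0 |
| 1% | 0.05 | 0.10 | 0.15 |
| 5% | 0.24 | 0.48 | 0.71 |
| 10% | 0.45 | 0.91 | 1.36 |

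For example, r = 10% and d = 10 give 10 × 0.10/1.10 = 0.91 points. The sign is unknown.

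Setting the shift to 1 point gives r = 1/(d−1). Earlier users would have to equal 25%, 11.1% or 7.1% of true initiators at d = 5, 10 or 15. More extreme inputs give more: if earlier users were 10% of the counted population and d were 20 points, the shift would be 0.10 × 20 = 2.0 points. The grid shows scale only and is not evidence about this study.

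**3. What a restricted estimate would lose.** Limiting index dates to 2016-01-01 onward keeps 731 of the 1,096 days. If initiation is uniform over the window, it drops 365/1,096 = 33.3% of true initiators. If initiation rises linearly from zero, it drops (365/1,096)² = 11.1%. The 2017 sub-group alone drops 731/1,096 = 66.7% or (731/1,096)² = 44.5%.

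**The case against.** The strongest reply is that misclassification needs at least one person who collected the drug before 2015 and again in the window, and nothing in the documents shows that one existed. If there was none, first in the extract equals first ever, and Tables 2 and 4 are right as written. The places where a reason for the start date would naturally stand are the ones that cannot be read. This part stands. A lost statement that no earlier collection was possible would close the point. A lost SPDR-based rule against prior use would not, because the legible collection period holds no earlier data to check it against.

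The plan also limits the effect. CVD status uses patient-register codes from 1997, so a later index date changes an individual's status little; what remains is a change in the mix of persons. The 2017 sub-group is reported separately. This stands too, but that sub-group does not replace the full-window estimate. It covers only a third of the window, and a gap between the two could equally reflect the guideline that the Introduction calls newly published and the reference list dates to 2017.

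Two stronger readings are tempting and not supported:

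- A reader might infer that Population 2 is known to contain earlier users, or that the primary prevalence is known to be biased. The documents give no count, and the number may be zero.
- A reader might see an inconsistent rule in the flowchart, since another line reports "The number of patients collecting Empagliflozin between 2015-01-01 and 2017-12-31 but who are not part of the broad population" while the question 2 line speaks of initiating. The two lines describe different groups, persons outside and inside the broad population, so the difference in verb shows no inconsistency.

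**Conclusion.** The point holds in conditional form. On the legible text, the extract cannot separate a first-ever collection from the first since 2015-01-01, and any earlier user who refills would enter Population 2 with an index date that is too late. The effect on the primary CVD prevalence lies between zero and probably under about 1 percentage point. That upper figure rests on assumed shares of earlier users and assumed prevalence differences, not on data in the documents. Any effect would be concentrated in 2015 index dates, and the 2017 sub-group is largely protected. Since nothing is tested, no decision threshold depends on it. This is an optional, inexpensive improvement of low severity.

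**What to change.** - In Table 2, start the SPDR extract for A10BK03 at the first recorded collection instead of 2015-01-01.
- In Tables 1 and 4, define Population 2 as persons in the broad population whose first-ever recorded collection falls between 2015-01-01 and 2017-12-31.
- Add one flowchart line for persons excluded because of an earlier collection, reported as zero if there are none.

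The cost is a slightly longer extract for one ATC code from a register already requested, and a few sentences of text. A data-approval step may be needed, which the documents do not address, and Population 2 may become slightly smaller.

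If earlier data cannot be obtained, add one sensitivity estimate of the primary prevalence limited to index dates from 2016-01-01, which guarantees at least 365 collection-free days, and show it beside the planned 2017 sub-group. It needs no new data. The report should say that it also drops the true 2015 initiators and still misses earlier users who paused for more than a year.
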